#### Quality Assurance and Confidentiality

First, the electronic data entry system “forces” responses to key questionnaire items (e.g., primary outcomes surveys) before allowing progression through the particular interview’s template, thereby minimizing missing data. For less critical items, delayed data entry is possible (though these data elements are non-essential to primary aims analyses). However, each time the study team logs into the secure data entry system, prompts appear on the welcome screen that show what data elements remain incomplete (as well as the time frame within which they must be entered) for all site participants.

The study PI will ensure the validity of the data system by examining electronic summary case report forms within the EDC system to ensure adequacy and accuracy of data collection as well as transcription to the database itself after enrollment of the first 5 participants. Agreement will be reviewed and discrepancies will be discussed.

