36. Trouble relaxing

Response is \*\*one\*\* of:

- Not at all
- A couple of days
- More than half the days
- Nearly every day

37. Being so restless that it is hard to sit still

Response is \*\*one\*\* of:

- Not at all
- A couple of days
- More than half the days
- Nearly every day

38. Becoming easily annoyed or irritable

Response is \*\*one\*\* of:

- Not at all
- A couple of days
- More than half the days
- Nearly every day

39. Feeling afraid as if something awful might happen

Response is \*\*one\*\* of:

- Not at all
- A couple of days
- More than half the days
- Nearly every day

40. The last few questions asked how often you were bothered by the problems. Now, please share how much distress the problem caused you:

Response is \*\*one position\*\* in this scale:

- 0 (No Distress)
- 10
- 20
- 30
- 40
- 50
- 60
- 70
- 80
- 90
- 100 (Serious Distress)

41. In the last week or so, how often have you experienced the following.

(This is an information screen that requires no response)

Click Next to continue.

42. I had sleep problems.

Response is \*\*one position\*\* in this scale:

- 1 (Never)
- 2
- 3
- 4
- 5
- 6
- 7 (Always)

43. I had nightmares.

Response is \*\*one position\*\* in this scale:

- 1 (Never)
- 2
- 3
- 4
- 5
- 6
- 7 (Always)

44. I had depression or felt dejected / downtrodden.

Response is \*\*one position\*\* in this scale:

- 1 (Never)
- 2
- 3
- 4
- 5
- 6
- 7 (Always)

45. I had jumpiness- I am easily frightened by sudden sounds or movements.

Response is \*\*one position\*\* in this scale:

- 1 (Never)
- 2
- 3
- 4
- 5
- 6
- 7 (Always)

46. I had the need to withdraw from others.

Response is \*\*one position\*\* in this scale:

- 1 (Never)
- 2
- 3
- 4
- 5
- 6
- 7 (Always)

47. I had irritability - I was easily agitated, annoyed and angered.

Response is \*\*one position\*\* in this scale:

- 1 (Never)
- 2
- 3
- 4
- 5
- 6
- 7 (Always)

48. I had frequent mood swings.

Response is \*\*one position\*\* in this scale:

- 1 (Never)
- 2
- 3
- 4
- 5
- 6
- 7 (Always)

49. I had a bad conscience, blamed myself, or had guilty feelings.

Response is \*\*one position\*\* in this scale:

- 1 (Never)
- 2
- 3
- 4
- 5
- 6
- 7 (Always)

50. I had a fear of places or situations that reminded me of the Intensive Care Unit.

Response is \*\*one position\*\* in this scale:

- 1 (Never)

- 2
- 3
- 4
- 5
- 6
- 7 (Always)

51. I had muscular tension.

Response is \*\*one position\*\* in this scale:

- 1 (Never)
- 2
- 3
- 4
- 5
- 6
- 7 (Always)

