52. The last few questions asked how often you were bothered by the problems. Now, please share how much distress the problem caused you:

Response is \*\*one position\*\* in this scale:

- 0 (No Distress)
- 10
- 20
- 30
- 40
- 50
- 60
- 70
- 80
- 90
- 100 (Serious Distress)

53. Over the last 2 weeks, how much have you been bothered by any of the following problems?

(This is an information screen that requires no response)

Click Next to continue.

54. Pain

Response is \*\*one\*\* of:

- Not bothered at all
- Bothered a little
- Bothered a lot

55. Difficulty concentrating

Response is \*\*one\*\* of:

- Not bothered at all
- Bothered a little
- Bothered a lot

56. Weakness

Response is \*\*one\*\* of:

- Not bothered at all
- Bothered a little
- Bothered a lot

57. Feeling your heart pound or race

Response is \*\*one\*\* of:

- Not bothered at all
- Bothered a little
- Bothered a lot

58. Shortness of breath (or other breathing problems)

Response is \*\*one\*\* of:

- Not bothered at all
- Bothered a little
- Bothered a lot

59. Stiffness in joints or muscles

Response is \*\*one\*\* of:

- Not bothered at all
- Bothered a little
- Bothered a lot

60. Constipation or diarrhea

Response is \*\*one\*\* of:

- Not bothered at all
- Bothered a little
- Bothered a lot

61. Nausea, gas or indigestion

Response is \*\*one\*\* of:

- Not bothered at all
- Bothered a little
- Bothered a lot

62. The last few questions asked how often you were bothered by the problems. Now, please share how much distress the problem caused you:

Response is \*\*one position\*\* in this scale:

- 0 (No Distress)
- 10
- 20
- 30
- 40
- 50
- 60
- 70
- 80
- 90
- 100 (Serious Distress)

63. In general, how would you rate your current quality of life?

Response is \*\*one position\*\* in this scale:

- 0 (Worst imaginable quality of life)
- 10
- 20
- 30
- 40
- 50
- 60
- 70
- 80
- 90
- 100 (Best imaginable quality of life)

78. How much do you agree or disagree with each statement?

(This is an information screen that requires no response)

Click Next to continue.

79. I never give up.

Response is \*\*one\*\* of:

- Totally disagree
- Disagree somewhat
- Neutral
- Agree somewhat
- Totally agree

80. I do everything to get well.

Response is \*\*one\*\* of:

- Totally disagree
- Disagree somewhat
- Neutral
- Agree somewhat
- Totally agree

81. I keep fighting to get better.

Response is \*\*one\*\* of:

- Totally disagree
- Disagree somewhat
- Neutral
- Agree somewhat
- Totally agree

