52. I had fear of places or situations that remind me of the Intensive Care Unit.

Response is \*\*one position\*\* in this scale:

- 1 (Never)
- 2
- 3
- 4
- 5
- 6
- 7 (Always)

53. I had muscular tension.

Response is \*\*one position\*\* in this scale:

- 1 (Never)
- 2
- 3
- 4
- 5
- 6
- 7 (Always)

54. The last few questions asked how often you were bothered by the problems. Now, please share how much distress the problem caused you:

Response is \*\*one position\*\* in this scale:

- 0 (No distress)
- 10
- 20
- 30
- 40
- 50
- 60
- 70
- 80
- 90
- 100 (Serious distress)

55. Over the last 2 weeks, how much have you been bothered by any of the following problems?

(This is an information screen that requires no response)

Click Next to continue.

56. Pain

Response is \*\*one\*\* of:

- Not bothered at all
- Bothered a little
- Bothered a lot

57. Difficulty concentrating

Response is \*\*one\*\* of:

- Not bothered at all
- Bothered a little
- Bothered a lot

58. Weakness

Response is \*\*one\*\* of:

- Not bothered at all
- Bothered a little
- Bothered a lot

59. Feeling your heart pound or race

Response is \*\*one\*\* of:

- Not bothered at all
- Bothered a little
- Bothered a lot

60. Shortness of breath (or other breathing problems)

Response is \*\*one\*\* of:

- Not bothered at all
- Bothered a little
- Bothered a lot

61. Stiffness in joints or muscles

Response is \*\*one\*\* of:

- Not bothered at all
- Bothered a little
- Bothered a lot

62. Constipation or diarrhea

Response is \*\*one\*\* of:

- Not bothered at all
- Bothered a little
- Bothered a lot

63. Nausea, gas, or indigestion

Response is \*\*one\*\* of:

- Not bothered at all
- Bothered a little
- Bothered a lot

64. The last few questions asked how often you were bothered by the problems. Now, please share how much distress the problem caused you:

Response is \*\*one position\*\* in this scale:

- 0 (No distress)
- 10
- 20
- 30
- 40
- 50
- 60
- 70
- 80
- 90
- 100 (Serious distress)

65. In general, how would you rate your current quality of life?

Response is \*\*one position\*\* in this scale:

- 0 (Worst imaginable quality of life)
- 10
- 20
- 30
- 40
- 50
- 60
- 70
- 80
- 90
- 100 (Best imaginable quality of life)

66. Currently I am able to:

(This is an information screen that requires no response)

Click Next to continue.

67. ... bathe myself em>(either a sponge bath, tub bath, or shower)

Response is \*\*one\*\* of:

- Need no help
- Need some help or unable to do

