- 7 (Always)

52. I had a fear of places or situations that remind me of the Intensive Care Unit.

Response is \*\*one position\*\* in this scale:

- 1 (Never)
- 2
- 3
- 4
- 5
- 6
- 7 (Always)

53. In the past week or so, I had muscular tension.

Response is \*\*one position\*\* in this scale:

- 1 (Never)
- 2
- 3
- 4 [default]
- 5
- 6
- 7 (Always)

54. The last few questions asked how often you were bothered by the problems. Now, please share show how much distress the problem caused you:

Response is \*\*one position\*\* in this scale:

- 0 (No distress)
- 10
- 20
- 30
- 40
- 50
- 60
- 70
- 80
- 90
- 100 (Serious distress)

55. Over the last 2 weeks, how much have you been bothered by any of the following problems?

(This is an information screen that requires no response)

Click Next to continue.

56. Pain

Response is \*\*one\*\* of:

- Not bothered at all
- Bothered a little
- Bothered a lot

57. Difficulty concentrating

Response is \*\*one\*\* of:

- Not bothered at all
- Bothered a little
- Bothered a lot

58. Weakness

Response is \*\*one\*\* of:

- Not bothered at all
- Bothered a little
- Bothered a lot

59. Feeling your heart pound or race

Response is \*\*one\*\* of:

- Not bothered at all
- Bothered a little
- Bothered a lot

60. Shortness of breath (or other breathing problems)

Response is \*\*one\*\* of:

- Not bothered at all
- Bothered a little
- Bothered a lot

61. Stiffness in joints or muscles

Response is \*\*one\*\* of:

- Not bothered at all
- Bothered a little
- Bothered a lot

62. Constipation or diarrhea

Response is \*\*one\*\* of:

- Not bothered at all
- Bothered a little
- Bothered a lot

63. Nausea, gas, or indigestion

Response is \*\*one\*\* of:

- Not bothered at all
- Bothered a little
- Bothered a lot

64. The last few questions asked how often you were bothered by the problems. Now, please share how much distress the problem caused you:

Response is \*\*one position\*\* in this scale:

- 0 (No distress)
- 10
- 20
- 30
- 40
- 50
- 60
- 70
- 80
- 90
- 100 (Serious distress)

65. In general, how would you rate your current quality of life?

Response is **\*\*one position\*\*** in this scale:

- 0 (Worst imaginable quality of life)
- 10
- 20
- 30
- 40
- 50 [default]
- 60
- 70
- 80
- 90
- 100 (Best imaginable quality of life)

66. Currently I am able to:

(This is an information screen that requires no response)

Click Next to continue.

67. ... bathe myself (either a sponge bath, tub bath, or shower)

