3.1 Primary Outcome(s)

Variable	Dataset	Description	Specifications

hads	Blueprint/Baseline	HADS total score at T0	Continuous
Hads	Blueprint/T1	HADS total score at T1	Continuous (may need to be derived from item scores HADS01—HADS14)
Score_hads	Blueprint/T2	HADS total score at T2	Continuous (may need to be derived from item scores HADS01—HADS14)
Score_hads	Blueprint/T3	HADS total score at T3	Continuous (may need to be derived from item scores HADS01—HADS14)
ptss	Blueprint/T1	PTSS total score at T1	Continuous (may need to be derived from item scores ptss_1—ptss_10)
Score_ptss	Blueprint/T2	PTSS total score at T2	Continuous (may need to be derived from item scores ptss_1—ptss_10)
Score_ptss	Blueprint/T3	PTSS total score at T3	Continuous (may need to be derived from item scores ptss_1—ptss_10)
D3mo_HADS	Blueprint/T3 Blueprint/T1	Change in HADS at 3 months	Derived as Score_hads(T3) - ???
D1mo_HADS	Blueprint/T2 Blueprint/T1	Change in HADS at 1 months	Derived as Score_hads(T2) - ???
D3mo_PTSS	Blueprint/T3 Blueprint/T1	Change in PTSS at 3 months	Derived as Score_ptss(T3) - ???
D1mo_PTSS	Blueprint/T2 Blueprint/T1	Change in PTSS at 1 months	Derived as Score_ptss(T2) - ???
ADLs/IADLs	T1, t2, t3		Not really an outcome but...
Systems Usability Scale	T1		
PHQ-10 physical symptom scale	T1, t2, t3		
Quality of life 100-point VAS	T1, t2, t3		
List		Feasibility	
Eligibility: 70% of positive screens Consent: 80% of eligible Randomized: 80% of consented Retention: 80% Adherence: 75% of tasks
 
***note that these need to be defined a bit more specifically

CSQ-8	`	Acceptability	

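### The T3 form presets one PTSS item at 4 and quality of life at 50, unlike T1 and T2; if untouched presets are saved, 3-month change in these two scores could be distorted

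*Protocol*

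**What the plan says.** **Muscular tension (the tenth PTSS item, scored 1 to 7).** In Protocol Appendix 3 the T1 form has "51. I had muscular tension" and the T2 form has "53. I had muscular tension", neither with a default. On the T3 form the item reads "In the past week or so, I had muscular tension", and the value 4 is tagged as the default.

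**Quality of life (one item, 0 to 100 in steps of 10).** T1 has "63. In general, how would you rate your current quality of life" and T2 has "65. In general, how would you rate your current quality of life", again without a default. T3 item 65 asks the same question with 50 tagged as the default.

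**Missing answers.** The Protocol's Quality Assurance and Confidentiality section says the data entry system forces "responses to key questionnaire items (e.g., primary outcomes surveys) before allowing progression". It does not mention preset values.

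**Use in the analysis.** Protocol section 4 names HADS and PTSS at 1 and 3 months as secondary outcomes. SAP 3.1 notes that the PTSS total "may need to be derived from item scores ptss_1—ptss_10". SAP 4.2 models HADS and PTSS over T1, T2 and T3, and Table 4 reports 3-month change by arm. Quality of life is listed in SAP 3.1 for T1 to T3, but it has no derived change variable and is not in the model. SAP section 4 promises the number of missing values for each variable. No rule in the SAP detects or handles default answers.

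**The concern.** A change score assumes that both visits were measured in the same way. Here one of the ten PTSS items, and the only quality-of-life item, appear to be collected under a different rule at T3 alone. A patient who passes over an item without a preset leaves it blank or is stopped by the forced-response check. If a preset is stored when nobody touches it, the same behaviour at T3 yields a mid-scale value that looks like an answer. The planned count of missing values would not include it.

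What is at stake is the within-arm 3-month PTSS change in SAP Table 4, and any description of quality of life at T3. The trial is an exploratory pilot, but its estimates are meant to inform a definitive trial.

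**Working it through.** **Step 1. Compare the forms.**

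| Item | T1 | T2 | T3 |
|---|---|---|---|
| Muscular tension | item 51, no default | item 53, no default | item 53, default 4 |
| Quality of life | item 63, no default | item 65, no default | item 65, default 50 |
| Other nine PTSS items | no default | no default | no default |
| HADS items | no default | no default | no default |

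The three distress-rating scales on the T3 form (items 42, 54 and 64) carry no default either. Both presets are exact midpoints: (1 + 7)/2 = 4 and (0 + 100)/2 = 50.

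**Step 2. Inputs.** The documents give the item scales and the ten-item PTSS sum, so the total runs from 10 × 1 = 10 to 10 × 7 = 70. They do not give the share of patients who would leave an item untouched (q), the true mean answer of those patients (m for muscular tension, v for quality of life) or the baseline SD of PTSS. These are assumptions below. There is no figure in the plan to reproduce. Steps 3 to 5 all suppose that an untouched preset is saved.

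**Step 3. Within-arm PTSS at T3.** For one person the largest error is 4 − 1 = +3 or 4 − 7 = −3 points, which is 3/60 = 5% of the range of the total. The shift in the mean is q × (4 − m):

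| q | m | Shift in mean PTSS |
|---|---|---|
| 10% | 2 | +0.2 |
| 20% | 2 | +0.4 |
| 30% | 1 | +0.9 |
| 50% | 1 | +1.5 |
| 100% | 1 | +3.0 (ceiling) |
| any | 4 | 0 |
| 20% | 5 | −0.2 |

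SAP 4.2 judges differences against half the baseline SD. For an assumed SD of 8 to 14 that is 4 to 7 points. A shift of 0.4 is 0.4/7 = 6% to 0.4/4 = 10% of it. The 3-point ceiling is 3/7 = 43% to 3/4 = 75%, but it requires every patient to leave the item untouched with a true answer of 1.

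**Step 4. Between-arm PTSS difference.** If q is the same in both arms, the constant 4 cancels. What is lost is q times the true arm difference on that one item. For an effect spread evenly over ten items this is q/10 of the total effect: 2% at q = 20%, and 10% at most. If q differs by arm, for example 10% against 30% with m = 2, the difference moves by (0.30 − 0.10) × (4 − 2) = 0.4 points.

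**Step 5. Quality of life at T3.** The shift is q × (50 − v). With q = 20% and v = 70 it is −4; with q = 50% and v = 80 it is −15; with v = 50 it is 0. The preset replaces the entire score, so one person's error can reach 50 points.

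**Step 6. HADS.** No HADS item carries a default, so the shift is 0.

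**The case against.** **The tags may not reflect the live form.** Appendix 3 looks like a raw app export. It has stray markup, the Week 1 check-in repeated under Week 2, and a duplicated answer option in T2 item 106. This stands as a reason to check the configuration first. It does not dispose of the point, because the two tags fall only on these items and only at T3.

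**A reader might infer that untouched answers are in fact stored and that 3-month change is therefore biased.** The documents do not support that. They do not say whether a preset counts as a response, whether it is saved without a touch, or whether untouched items are flagged.

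**A reader might infer a bias toward worsening.** That holds only if true answers lie below the midpoint. At 4 there is no shift, and above 4 it reverses.

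**A reader might infer that the bias differs by arm.** Protocol section 3 has staff administer the Arm 3 surveys by email or phone, which could leave the preset acting mainly in the app arms. But note (c) to the Appendix 1 schedule has all participants complete surveys 1 to 3 in the app whatever their arm, and section 13 expects most data to be self-entered there. The documents conflict on this, so a differential effect is possible but not established.

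**The reworded stem is immaterial.** The block header on all three forms already sets the recall period at about the last week. The added phrase therefore does not alter what "I had muscular tension" asks. It is worth aligning only for consistency.

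**The scope is narrow.** This stands: HADS is untouched, PTSS is exposed through one item in ten, and quality of life is neither a named secondary outcome in Protocol section 4 nor a modelled one in the SAP.

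**Conclusion.** The T3 form presets two items that T1 and T2 leave open. That much is plain from the forms. Any effect on results is conditional on an untouched preset being saved.

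Under that condition, within-arm 3-month PTSS change could be off by at most 3 points per person in either direction. The shift in the mean would be a few tenths of a point under moderate assumptions (+0.4 at q = 20%, m = 2). Quality of life at T3 could be off by several points on average. HADS is unaffected. The PTSS arm differences in Table 4 would change little unless the untouched share differs by arm. All values of q, m, v and the SD are assumptions.

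This is a modest point and does not threaten the trial's main purpose. It merits action because the possible artefact falls on a named outcome, the plan as written could not detect it, and the remedy is cheap.

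**What to change.** 1. Have the sponsor check the live T3 configuration. If it has no presets, one line of confirmation closes the matter.
2. If the presets exist, remove both or require an active response before the patient can move on. Use the T1 and T2 stem for item 53.
3. If T3 data were already collected with the presets, add to SAP 4.2 a sensitivity analysis of PTSS change using the nine items without a preset, scored the same way at T1, T2 and T3. The nine-item score runs from 9 to 63, so its half-SD yardstick should come from its own baseline SD. The SAP describes randomization in the past tense, so such data may exist.
4. Report, by arm, how many T3 values are exactly 4 on item 53 and exactly 50 on quality of life. Use app interaction data where available, because the value alone cannot separate a real answer from an untouched one.

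The cost is a small app change and one extra analysis.

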#### J. Weekly Check-Ins

### Week 1 Check In

# Week 1 Check In

## Week 1 Check In

Time for the 1-minute Blueprint weekly mini-survey!

1. Please select the response that describes how you felt in the past week.

(This is an information screen that requires no response)

Click Next to continue

2. I feel tense or wound up

Response is \*\*one\*\* of:

- Not at all
- Time to time, occasionally
- A lot of the time
- Most of the time

3. I still enjoy the things I used to enjoy

Response is \*\*one\*\* of:

- Definitely as much
- Not quite so much
- Only a little
- Hardly at all

4. I get a frightened feeling like something awful is about to happen

Response is \*\*one\*\* of:

- Not at all
- A little, but it doesn't worry me
- Yes, but not too badly
- Very definitely and quite badly

5. I can laugh and see the funny side of things

Response is \*\*one\*\* of:

- As much as I always could
- Not quite so much now
- Definitely not so much now
- Not at all

6. Worrying thoughts go through my mind

Response is \*\*one\*\* of:

- Only occasionally
- From time to time but not too often
- A lot of the time
- A great deal of the time

7. I feel cheerful

Response is \*\*one\*\* of:

- Most of the time
- Sometimes
- Not often
- Not at all

8. I can sit at ease and feel relaxed

Response is \*\*one\*\* of:

- Definitely
- Usually
- Not often
- Not at all

9. I feel as if I am slowed down

Response is \*\*one\*\* of:

- Not at all
- Sometimes
- Very often
- Nearly all of the time

10. I get a sort of frightened feeling like butterflies in the stomach

Response is \*\*one\*\* of:

- Not at all
- Occasionally
- Quite often
- Very often

11. I have lost interest in my appearance

Response is \*\*one\*\* of:

- I take just as much care as ever
- I may not take quite as much care
- I don't take as much care as I should
- Definitely

12. I feel restless as if I have to be on the move

Response is \*\*one\*\* of:

- Not at all
- Not very much
- Quite a lot
- Very much indeed

13. I look forward with enjoyment to things

Response is \*\*one\*\* of:

- As much as I ever did
- A bit less than I used to
- Definitely less than I used to
- Hardly at all

14. I get sudden feelings of panic

Response is \*\*one\*\* of:

- Not at all
- Not very often
- Quite often
- Very often indeed

15. I can enjoy a good book or radio or TV program

Response is \*\*one\*\* of:

- Often
- Sometimes
- Not often
- Very seldom

16. How confident do you feel using progressive muscle relaxation?

This question includes an image.

Response is \*\*one position\*\* in this scale:

- 0 (Not at all confident)
- 10
- 20
- 30
- 40
- 50
- 60
- 70

- 80
- 90
- 100 (Extremely confident)

17. That's okay. It is normal to feel a little unsure at first with progressive muscle relaxation. Most people find that their confidence improves with practice. You can do it!

(This is an information screen that requires no response)

18. You are off to a great start. It is normal to feel this way about progressive muscle relaxation at this point. Remember to practice daily. Great work!

(This is an information screen that requires no response)

19. : Wow, you really have the hang of progressive muscle relaxation. Remember to keep practicing. Great work!

(This is an information screen that requires no response)

20. How helpful is using progressive muscle relaxation

This question includes an image.

Response is \*\*one position\*\* in this scale:

- 0 (Not at all helpful)
- 10
- 20
- 30
- 40
- 50
- 60
- 70
- 80
- 90
- 100 (Extremely helpful)

21. That's OK. It often takes time to get comfortable with a new skill and see its benefits. Most people find that the more they practice progressive muscle relaxation, the more helpful they find it. Give it a try for awhile longer and see what you think.

(This is an information screen that requires no response)

22. That's great. It sounds like progressive muscle relaxation might be a useful tool for you. Keep practicing—the more you use it, the more helpful it is likely to be.

(This is an information screen that requires no response)

23. Great! It sounds like progressive muscle relaxation is a really useful tool for you. Keep practicing - the more you use it, the more helpful it is likely to be.

(This is an information screen that requires no response)

24. How confident do you feel using pleasant imagery

This question includes an image.

Response is **\*\*one position\*\*** in this scale:

- 0 (Not at all confident)
- 10
- 20
- 30
- 40
- 50
- 60
- 70
- 80
- 90
- 100 (Extremely confident)

25. That's okay. It is normal to feel a little unsure at first with pleasant imagery. Most people find that their confidence improves with practice. You can do it.

(This is an information screen that requires no response)

26. You are off to a great start. It is normal to feel this way about pleasant imagery at this point. Remember to practice daily. Great work!

(This is an information screen that requires no response)

27. Wow, you really have the hang of pleasant imagery. Remember to keep practicing. Great work!

(This is an information screen that requires no response)

28. How helpful is using pleasant imagery?

This question includes an image.

Response is **\*\*one position\*\*** in this scale:

- 0 (Not at all helpful)
- 10
- 20
- 30
- 40
- 50
- 60
- 70
- 80

- 90
- 100 (Extremely helpful)

29. That's OK. It often takes time to get comfortable with a new skill and see its benefits. Most people find that the more they practice pleasant imagery, the more helpful they find it. Give it a try for awhile longer and see what you think.

(This is an information screen that requires no response)

30. That's great. It sounds like pleasant imagery might be a useful tool for you. Keep practicing—the more you use it, the more helpful it is likely to be.

(This is an information screen that requires no response)

31. Great! It sounds like pleasant imagery is a really useful tool for you. Keep practicing - the more you use it, the more helpful it is likely to be.

(This is an information screen that requires no response)

32. Thank you!

(This is a score screen that requires no response)

You have completed the assessment. Click Next to submit your responses.

